5.2 Treatment Period

During the Treatment Period subjects will receive cabozantinib for 12 weeks or until the occurrence of unacceptable drug-related toxicity or for other reason(s) for subject withdrawal as described in Section 3. Subjects should be instructed to immediately inform the investigator or study team member of any AEs.

The following schedule of assessments applies to all subjects (Table 5-1). More frequent assessments should be obtained if clinically indicated.

Table 5-1: On Study Assessments

	Study Treatment Period			Post-Treatment Period	Long-Term follow up Period
	Screening ^a	Week 1 Day 1 ^m	Week 2, 6 Day 1 (± 5 days)	Within 14 days after last dose	
Informed consent	X				
Demographics	X				
Medical and cancer history/demographics	X				
Physical examination	X	X	X	X	
Height	X				
Weight	X	X	X	X	
Vital signs	X	X	X	X	
ECOG performance status	X	X	X	X	
Clinical laboratory tests ^b	X	X	X	X	
Urinalysis and UPCR	X	X	X ^c	X	
PT/INR, PTT	X	X	X ^c		
TFTs (TSH, free T3, free T4)	X		X ^c	X	
12-lead ECG	X	X	X ^c	X	
ECHO or MUGA ^j	X				
Cabozantinib administration		X (daily)	X (daily)		
Urine Pregnancy test ^l	X	X	X ^c	X	
Tumor assessment ^d	X		X ^c	X ⁿ	X ^e
Concomitant medications		X	X	X	
Adverse events		Continuous		X	
Follow-up				X	X ^f
Blood for correlative studies		X	X ^c	X	X ^k
Pathologic Confirmation of clear cell component	X				
Quality of life questionnaires ^h		X	X ^c	X	
Frailty assessment ^l		X	X ^c	X	
Sarcopenia assessment		X	X ^c	X	
Kidney Surgery				X ^g	

ECG, electrocardiogram; ECOG, Eastern Cooperative Oncology Group; PT/INR, prothrombin time/International Normalized Ratio; PTT, partial prothrombin time, TFT, thyroid function test; UPCR, urine protein/creatinine ratio

^a Screening will be done within 28 days before the 1st dose.

^b laboratory tests should include a standard hematology panel (CBC, differential, platelets) and chemistry panel (albumin, alkaline phosphatase, ALT, amylase, AST, bicarbonate, bilirubin, blood urea nitrogen, calcium, chloride, creatinine, γ -glutamyltransferase [GGT], glucose, lactate dehydrogenase, lipase, magnesium, phosphorus, potassium, sodium, total protein). CRP

^c Week 6 only

^d All sites of known disease must be assessed.

^e Surveillance scan after surgery will be obtained per investigator.

^fPatients in long term follow-up can be seen by medical oncology or urology team, have chart reviewed, or phone call to determine current status every 3 months. (+/- 14 days).

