5.3 Post-Treatment Period

Subjects will return to the study site within 14 days after their last dose of cabozantinib to complete end-of-study assessments. Laboratory, imaging and physical examinations will be performed. Remaining study treatment will be returned by the subject, and treatment compliance will be documented. Additional follow-up will occur for subjects with AEs related to study treatment that are ongoing at the time of this visit, and for subjects with SAEs related to study treatment that occur after the time of this visit.

This period includes intraoperative and post-operative assessments. Patients will wait a minimum of 28 days (washout period) from the last dose of cabozantinib prior to surgical resection. Patients will be assessed for intraoperative and post-operative complications using the universally recognized Clavien Dindo perioperative classification of adverse events (13). Specifically, we will examine endpoints including, but not limited, chylous ascites, pulmonary embolism, ileus, bleeding, superficial wound dehiscence, fascial dehiscence, pleural effusion, pneumonia, urinary retention, gastroparesis, anemia, and post-operative delirium. We will also collect data regarding procedure type, i.e. radical nephrectomy, partial nephrectomy, and rate of conversion from radical to partial nephrectomy.

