6.3.2 Guidelines for Management of Potential Adverse Events

Subjects will be monitored for AEs from the time of signing informed consent through their last follow-up visit (30 days after the date of the last dose of cabozantinib treatment.) Subjects will be instructed to notify their physician or other study team member immediately at the onset of any AE. Seriousness, severity grade, and relationship to study treatment of AEs will be determined by the investigator. AE severity will be graded by the investigator in accordance with CTCAE v.4.0.

Management of severe or intolerable adverse reactions may require temporary dose reduction and/or interruption for cabozantinib.

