8 SAFETY

8.1 Adverse Events and Laboratory Abnormalities

8.1.1 Adverse Events (AEs)

An AE is any untoward medical occurrence in a patient or clinical trial subject administered a medicinal product and which does not necessarily have a causal relationship with this treatment.

An adverse event can therefore be any unfavorable and unintended sign (e.g. an abnormal laboratory finding), symptom, or disease temporarily associated with the use of a medicinal product, whether or not considered related to the medicinal product. An adverse event can arise from any use of the drug (e.g. off-label use, use in combination with another drug) and with any route of administration, formulation, or dose, including an overdose. This definition also includes AEs associated with medication errors and uses of the investigational product outside what is in the protocol, including misuse and abuse. Pre-existing medical conditions that worsen during the study should be recorded as AEs. Abnormal laboratory values, ECG findings, or vital signs are to be recorded as AEs if they meet the criteria described in in Section 6.

All untoward events that occur after informed consent through 30 days after the decision to discontinue study treatment (or the date the subject is deemed to be a screen failure) are to be recorded by the investigational site. This requirement includes AEs from unscheduled as well as scheduled visits.

The investigator (or physician designee) is responsible for verifying and providing source documentation for all adverse events and assigning the attribution for all adverse events for subjects enrolled.

Attribution is the relationship between an adverse event or serious adverse event and the study treatment. Attribution will be assigned as follows:

- Definite – The AE *is clearly related* to the study treatment.
- Probable – The AE *is likely related* to the study treatment.
- Possible – The AE *may be related* to the study treatment.
- Unlikely – The AE *is doubtfully related* to the study treatment.
- Unrelated – The AE *is clearly NOT related* to the study treatment.

Adverse event terms recorded on the CRFs will be mapped to preferred terms using the Medical Dictionary for Regulatory Activities (MedDRA). Seriousness, severity grade, and relationship to study treatment will be assessed by the investigator. Severity grade will be defined by the current version of the National Cancer Institute (NCI)-Common Terminology Criteria for Adverse Events (CTCAE).

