8.1.3 Relationship to Study Treatment

Assessment of the relationship of the AE to the study treatment by the investigator is based on the following two definitions:

- Not Related: A not-related AE is defined as an AE that is not associated with the study treatment and is attributable to another cause or there is no evidence to support a causal relationship;
- Related: A related AE is defined as an AE where a causal relationship between the event and the study treatment is a reasonable possibility. A reasonable causal relationship is meant to convey that there are facts (e.g., evidence such as dechallenge/rechallenge) or other clinical arguments to suggest a causal relationship between the AE and study treatment. Possibly and probably related AEs should be documented as related.

8.1.4 Serious Adverse Event Reporting:

As soon as an investigator becomes aware of an AE that meets the definition of ‘serious,’ this must be promptly documented on an SAE Report Form and in the electronic database (OnCore). All SAEs must be assessed by PI in order to determine reporting criteria to regulatory authorities

and include the following: (i) all SAEs that occur after starting cabozantinib and through 30 days after the decision to discontinue study treatment and (ii) any SAEs assessed as related to study treatment or study procedures, from the time of informed consent, even if the SAE occurs more than 30 days after the decision to discontinue study treatment.

All SAEs that are assessed by the PI as **related** to drug or study procedure and all pregnancy/lactation reports regardless of outcome must be sent to Exelixis within one (1) business day of the PI's knowledge of the event. The reports must be sent to [contact] or [contact].

- The PI will perform adequate due diligence with regard to obtaining follow-up information on incomplete reports. All follow-up information must be sent to Exelixis within one (1) business day of the PI's receipt of the new information. Upon Exelixis request, the PI will query for follow-up information.

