8.2 Other Safety Considerations

8.2.1 Laboratory Data

All laboratory data required by this protocol and any other clinical investigations should be reviewed. Any abnormal value that leads to a change in subject management (e.g., dose reduction or delay or requirement for additional medication or monitoring) or that is considered

to be of clinical significance by the investigator should be reported as an AE or SAE as appropriate.

8.2.2 *Pregnancy/Lactation Exposure*

If a subject becomes pregnant during the study, she will be taken off study treatment and will be followed through the end of her pregnancy. Pregnancy (in subject or partner) or lactation exposure, although not an SAE, should be reported to Exelixis. Forms will be provided to the study sites upon request. The outcome of a pregnancy (for a subject or for the partner of a subject) and the medical condition of any resultant offspring must be reported to Exelixis. Any birth defect or congenital anomaly must be reported as an SAE, and any other untoward events occurring during the pregnancy must be reported as AEs or SAEs, as appropriate.

8.2.3 *Medication Errors/Overdose*

Any overdose, or study drug administration error that results in an AE, even if it does not meet the definition of serious, requires reporting within one (1) business day to Exelixis.

8.2.4 *Follow-Up of Adverse Events*

Any related SAEs or any AEs assessed as related that led to treatment discontinuation, including clinically significant abnormal laboratory values that meet these criteria, ongoing 30 days after the decision to discontinue study treatment must be followed until either resolution of the event or determination by the investigator that the event has become stable or irreversible. This follow-up guidance also applies to related SAEs that occur more than 30 days after the decision to discontinue study treatment. The status of all other continuing AEs will be documented as of 30 days after the decision to discontinue study treatment.

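### Section 6.3.2 ends AE monitoring at a visit 30 days after the last dose, but Table 5-1 and Section 5.3 list no such visit and make their last AE check by day 14

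*Combined protocol and SAP*

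**What the plan says.** **The collection window.** Section 6.3.2 has subjects monitored for AEs from consent "through their last follow-up visit (30 days after the date of the last dose of cabozantinib treatment". Section 8.1.1 requires the recording of "All untoward events that occur after informed consent through 30 days after the decision to discontinue study treatment", without regard to seriousness or relatedness, and includes AEs from unscheduled visits. Section 8.1.4 covers "all SAEs that occur after starting cabozantinib and through 30 days after the decision to discontinue study treatment". Section 8.2.4 sets rules for related SAEs and for related AEs that led to discontinuation, and then adds: "The status of all other continuing AEs will be documented as of 30 days after the decision to discontinue study treatment".

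**The schedule.** In Table 5-1 (Section 5.2) the adverse-event row reads as continuous during treatment. It then has one mark, in the post-treatment column headed "Within 14 days after last dose". There is no 30-day column, and the long-term column has no AE mark. Section 5.3 describes the same visit: "Subjects will return to the study site within 14 days after their last dose of cabozantinib to complete end-of-study assessments". On what follows, it says: "Additional follow-up will occur for subjects with AEs related to study treatment that are ongoing at the time of this visit", and it makes the same provision for related SAEs that arise after the visit.

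**Surgery.** Surgery takes place at least 28 days after the last dose, with no upper limit stated. Section 5.3 adds: "Patients will be assessed for intraoperative and post-operative complications using the universally recognized Clavien Dindo perioperative classification of adverse events".

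**The concern.** The protocol defines a 30-day AE window and names a visit that closes it, but the schedule that staff work from stops by day 14. Take a new, non-serious, unrelated AE that starts on day 20. Section 8.1.1 requires it to be recorded, yet neither Table 5-1 nor Section 5.3 provides a contact at which anyone would ask about it. An unrelated AE still continuing at the 14-day visit needs a day-30 status under Section 8.2.4, and no listed contact obtains it.

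Safety and tolerability is a secondary objective (Section 2), and Section 9 summarises each AE by count and percentage. With at most 17 patients, one patient whose event is missed moves a reported rate by 1/17, about 6 percentage points. The days concerned fall mostly in the pre-surgical washout.

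**Working it through.** The plan gives no figure of its own to reproduce. The check is a day count, followed by a comparison of anchor dates.

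**Inputs**
- Day *v* of the last AE check: 0 to 14 after the last dose (Table 5-1, Section 5.3).
- End of the window: day 30 after the last dose (Section 6.3.2), or day 30 after the decision to discontinue (Sections 8.1.1, 8.1.4, 8.2.4).
- Day *s* of surgery: 28 or later (Table 5-1 footnote g, Section 5.3).

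**Step 1. Window counted from the last dose, Table 5-1 alone.** Days without a listed AE check = 30 − *v*.
- *v* = 14: 30 − 14 = 16 days (days 15 to 30), or 16/30 = 53% of the window
- *v* = 7: 30 − 7 = 23 days
- *v* = 0: 30 − 0 = 30 days

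**Step 2. Credit for the perioperative assessment.** If surgery falls inside the window, treat its complication assessment as covering day *s* onwards. Uncovered days = *s* − 1 − *v*.
- *s* = 28, *v* = 14: 28 − 1 − 14 = 13 days (days 15 to 27)
- *s* = 28, *v* = 0: 28 − 1 − 0 = 27 days

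If surgery is after day 30, the Step 1 figures stand.

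**Step 3. Window counted from the decision to discontinue.** Let the decision fall *k* days after the last dose. The window then ends on day 30 + *k*, and the gap after a day-14 visit is 30 + *k* − 14 = 16 + *k*. The documents do not give *k*, and they do not define the decision date for a patient who completes 12 weeks. The values below are assumptions; 42 corresponds to a 6-week interruption (Section 6.3) that ends in discontinuation.

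| *k* (days) | Window ends, days from last dose | Gap after a day-14 visit |
|---|---|---|
| −7 | 23 | 9 |
| 0 | 30 | 16 |
| 7 | 37 | 23 |
| 42 | 72 | 58 |

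The 16 days therefore belong to the last-dose window of Section 6.3.2. They are not a floor for the Section 8 windows.

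**Step 4. After the fix.** A contact on day 30 after the last dose leaves 30 − 30 = 0 days beyond the last listed check. Under the Section 8 anchor it leaves (30 + *k*) − 30 = *k* days when *k* is positive. Adding a contact without settling the anchor does not close the gap.

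**The case against.** The strongest reply is that the window is already provided for and only a table column is missing. Section 6.3.2 names the day-30 visit, Section 8.1.1 imposes the duty to record, and Sections 5.2 and 6.3.2 tell subjects to report AEs at once. An event between contacts can be entered later with its onset date, so days without a visit are not lost days. The interval on treatment from week 6 to the end of week 12 is also longer than 16 days. All of this stands, and it rules out reading the gap as a period in which AEs go uncollected. What remains is that capture after the 14-day visit relies on spontaneous or unscheduled reporting, in a schedule that calls that visit the end of study.

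A second reply is that the post-treatment column of Table 5-1 is not confined to 14 days, since it also holds surgery and a scan allowed up to day 28. But those two entries carry footnotes that move them outside the 14 days, and the AE mark carries none. The table was read from PDF, so its layout deserves some caution, but the text of Section 5.3 agrees with this reading.

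Three stronger inferences are tempting, and the documents do not support them:
- A reader might infer that Section 5.3 restricts later follow-up to related events. It says that follow-up will occur for those subjects; it does not say that others are excluded.
- A reader might infer that the next contact after day 14 is the 3-monthly follow-up. Surgery and its complication assessment come first.
- A reader might infer that sites would report different AE rates depending on which section they follow. The documents identify one institution; the references to study sites and multi-center studies are generic.

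**Conclusion.** The inconsistency is real. Section 6.3.2 refers to a visit that Table 5-1 and Section 5.3 do not contain, and Section 8 sets a 30-day window from a different starting date. Counted from the last dose, Table 5-1 leaves at least 16 days without an AE check. This falls to 13 days if surgery is on day 28 and its complication assessment is taken to cover AEs from then on.

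The consequence is a risk of under-ascertainment in the descriptive AE frequencies. The number of events missed cannot be estimated from the documents, and the share of days should not be read as a share of events. The primary endpoint and the two-stage design are unaffected. The point is worth correcting because the protocol already requires these data and the correction is small.

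**What to change.** 1. Add the Section 6.3.2 day-30 AE contact to Table 5-1. A phone call is enough, or the pre-operative contact can serve if it falls at day 30. A pre-operative contact before day 30 would not close the window.
2. State in Section 5.3 that all AEs, whatever their relatedness or seriousness, are collected to the end of the 30-day window. Keep the existing provision for longer follow-up of related events.
3. Use one anchor date, either the last dose or the decision to discontinue, in Sections 6.3.2, 8.1.1, 8.1.4 and 8.2.4. Time the new contact from that date. If the decision date is kept, define it for patients who complete 12 weeks.

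The cost is one table column, a few aligned sentences, and at most one brief contact per patient (17 at most). No endpoint, sample size or treatment rule changes.

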5.3 Post-Treatment Period

Subjects will return to the study site within 14 days after their last dose of cabozantinib to complete end-of-study assessments. Laboratory, imaging and physical examinations will be performed. Remaining study treatment will be returned by the subject, and treatment compliance will be documented. Additional follow-up will occur for subjects with AEs related to study treatment that are ongoing at the time of this visit, and for subjects with SAEs related to study treatment that occur after the time of this visit.

This period includes intraoperative and post-operative assessments. Patients will wait a minimum of 28 days (washout period) from the last dose of cabozantinib prior to surgical resection. Patients will be assessed for intraoperative and post-operative complications using the universally recognized Clavien Dindo perioperative classification of adverse events (13). Specifically, we will examine endpoints including, but not limited, chylous ascites, pulmonary embolism, ileus, bleeding, superficial wound dehiscence, fascial dehiscence, pleural effusion, pneumonia, urinary retention, gastroparesis, anemia, and post-operative delirium. We will also collect data regarding procedure type, i.e. radical nephrectomy, partial nephrectomy, and rate of conversion from radical to partial nephrectomy.

5.4 Long Term Follow-up Period

After kidney surgery, patients will enter the long term follow-up period. Data to determine a patient's current status may be collected from clinic visits with either medical oncology or urology ,chart review, or phone call every 3 months (+/- 14 days) until disease recurrence, initiation of new antineoplastic or investigational therapy, whichever occurs first. During this period, surveillance imaging will be obtained per investigator. A final blood sample for correlative studies will be collected after surgery. Patients removed from study for unacceptable adverse event(s) will be followed until resolution or stabilization of the adverse event.

Long-term follow-up continues until the patient's withdrawal of consent or loss to follow up, death, or study termination.

A participant will be considered lost to follow-up if he fails to return for three scheduled visits and is unable to be contacted by the study site staff after three attempts at contact by phone.

The following actions must be taken if a participant fails to return to the clinic for a required study visit:

- The site will attempt to contact the participant and reschedule the missed visit and counsel the participant on the importance of maintaining the assigned visit schedule and ascertain if the participant wishes to and/or should continue in the study.
- Before a participant is deemed lost to follow-up, the investigator or designee will make every effort to regain contact with the participant (where possible, 3 telephone calls and, if necessary, a certified letter to the participant's last known mailing address or local equivalent methods). These contact attempts should be documented in the participant's medical record or study file.
- Should the participant continue to be unreachable, patient will be considered to have withdrawn from the study with a primary reason of lost to follow-up.

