2 STUDY OBJECTIVES AND ENDPOINTS

The objectives of this study are as follows:

Primary objective:

- To assess the objective response rate (complete and partial responses), following the administration of cabozantinib for 12 weeks in patients with locally advanced biopsy-proven non-metastatic ccRCC prior to undergoing surgery.

Secondary Objectives:

- To assess the safety, and tolerability of neoadjuvant cabozantinib.
- To determine the clinical outcome (DFS, OS) of patients with non-metastatic ccRCC who treated with neoadjuvant cabozantinib.
- To evaluate the surgery related outcomes.
- To evaluate correlative studies, including biomarkers, quality of life, and frailty/sarcopenia assessment of patients with non-metastatic ccRCC who are treated with neoadjuvant cabozantinib.

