9 STATISTICAL CONSIDERATIONS

The primary outcome is objective response rate (complete and partial responses) at week 12 after the administration of cabozantinib. The Simon's two-stage design will be adopted for a possible early termination for futility. We hypothesize that there is > 24% response rate at 12-week and a rate < 5% will be considered as futility. In the first stage, 11 patients will be accrued (this does not include screen failures), and if there is no responses among them, the study will be stopped for futility. Otherwise, additional 6 patients will be accrued for a total of 17 patients. The null hypothesis will be rejected if there are 3 or more responses in 17 patients. The design yields a type I error rate of 0.05 and power of 80% when the true response rate is 24%. The final response rate will be estimated with 95% confidence interval by binomial test.

The safety profile of the treatment will be documented and summarized by summary statistics as frequency and percentage for each AE. We will do safety assesment after the first 6 patients without pausing the enrollment.

For disease free survival (DFS), which was defined as the interval between time of surgery and the first tumor recurrence, or death. Patients will be censored at time of last follow-up. For overall survival, death from any cause will be defined as the event. Patients will be censored at time of last follow-up. Overall survival (OS) and disease free survival (PFS) will be estimated

with the Kaplan-Meier method. The DFS and OS of each patient group at specific time points, such as 6 months, 1 year, and 3 year, etc. will be also estimated along with 95% CI.

For the biomarker study, descriptive statistics will be first used to summarize biomarker endpoints, including analyses of tumor biopsies. Biomarker data will also be displayed graphically, where appropriate. Depending on whether data is normally distributed, t-test or Wilcoxon rank sum test will be used to compare each biomarker between any two groups stratified by response or other factors, respectively. Logistics regression model will be further employed to test the adjusted effect of biomarker on the response rate after adjusting for other factors.

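### Section 5.4 contradicts itself and Table 5-1 footnote f on when 3-monthly status contact ends; if the narrower sentence is followed and later deaths go unrecorded, Kaplan-Meier OS is likely biased upward

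*Combined protocol and SAP*

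**What the plan says.** Three passages of the combined protocol and SAP bear on how long status is collected after surgery.

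- Section 5.4, first paragraph: status comes from clinic visits, chart review or phone calls "every 3 months (+/- 14 days) until disease recurrence, initiation of new antineoplastic or investigational therapy, whichever occurs first".
- Section 5.4, second paragraph: "Long-term follow-up continues until the patient's withdrawal of consent or loss to follow up, death, or study termination". No contact interval is given.
- Table 5-1, footnote f: patients in long-term follow-up may be seen, or "have chart reviewed, or phone call to determine current status every 3 months". No stop at recurrence or new therapy is given.

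Section 5.4 adds that a participant is "considered lost to follow-up if he fails to return for three scheduled visits" and cannot be reached after three phone attempts.

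On the analysis side, Section 2 lists a secondary objective: "To determine the clinical outcome (DFS, OS) of patients with non-metastatic ccRCC". Section 9 says: "For overall survival, death from any cause will be defined as the event. Patients will be censored at time of last follow-up". It defines DFS as "defined as the interval between time of surgery and the first tumor recurrence, or death". Both endpoints are estimated "with the Kaplan-Meier method. The DFS and OS of each patient group at specific time points", with 6 months, 1 year and 3 years given as examples, each with a 95% CI.

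**The concern.** The only sentence in Section 5.4 that sets a contact interval also ends it at recurrence or new therapy. A site working from that sentence would have no further scheduled contact with a patient whose disease has returned. That patient's last follow-up would be the recurrence visit, and Section 9 would censor OS there. Such censoring is informative, because patients leave the risk set when their risk of death is expected to rise. If no patient dies before recurrence, the OS curve stays at 100% and the usual Greenwood interval has zero width, so the error would look like precision.

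DFS is not harmed by a stop at recurrence, which is its event. A stop at new therapy without recurrence is different: it ends follow-up before either DFS event has occurred.

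What is at stake is a descriptive secondary endpoint. The response-rate analysis and the two-stage stopping rule do not use these data.

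**Working it through.** **The passages side by side**

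| Passage | Interval | Ends at |
|---|---|---|
| Section 5.4, first paragraph | 3 months | recurrence or new therapy |
| Section 5.4, second paragraph | none given | withdrawal, loss, death or study termination |
| Table 5-1, footnote f | 3 months | no end given |

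The second and third together give 3-monthly status until death. The first does not. Nothing says which prevails.

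**Size from the planned sample alone**

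The plan states no expected OS, so there is no OS figure to reproduce. Take n = 17 (Section 9), the narrower sentence followed, later deaths unrecorded, and all patients otherwise followed to time t. If m patients die after recurrence and none before it:

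- true OS = (17 - m)/17; Kaplan-Meier OS = 100%; overstatement = m/17
- m = 1: 5.9 points; m = 2: 11.8; m = 3: 17.6

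Deaths without recurrence reduce this. Suppose 8 patients recur, 2 of them die, and later 1 of the other 9 dies without recurrence. Kaplan-Meier OS = 8/9 = 88.9%; true OS = 14/17 = 82.4%; difference 6.5 points.

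**Illustration over time (assumed rates, not in the documents)**

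Constant hazards, time from surgery, every recurring patient censored at recurrence. Assumed ranges: 3-year DFS (D) 50-70%; death without recurrence (d) 2-5% by 3 years; median survival after recurrence (M) 21.4-60 months.

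- λ = -ln(D)/36; μ = -ln(1 - d)/36; r = λ - μ; k = ln 2 / M
- true OS(t) = exp(-λt) + r[exp(-kt) - exp(-λt)]/(λ - k)
- Kaplan-Meier target when censored at recurrence = exp(-μt)
- sampling SE = √{OS(1 - OS)/17}

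Upper end at 36 months (D = 50%, d = 2%, M = 21.4): λ = 0.01925, μ = 0.00056, r = 0.01869, k = 0.03239. True OS = 0.500 + 0.01869 × (0.3116 - 0.500)/(0.01925 - 0.03239) = 0.768. Kaplan-Meier target = 0.980. Overstatement 21.2 points.

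Lower end at 36 months (D = 70%, d = 5%, M = 60): true OS 0.908, Kaplan-Meier target 0.950, overstatement 4.2 points.

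| Time | Overstatement (points) | SE of OS at n = 17 (points) |
|---|---|---|
| 6 months | 0.1-1.0 | 1.7-3.2 |
| 12 months | 0.6-3.5 | 2.8-5.2 |
| 24 months | 2-11 | 4.7-8.4 |
| 36 months | 4-21 | 6.2-10.4 |

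**Direction.** If the death hazard is the same before and after recurrence, the bias is zero. In this model it reverses only if M exceeds ln 2/μ: 486 months at d = 5%, 1,235 months at d = 2%.

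**Partial loss.** A separate simulation at n = 17 assumed a recurrence hazard equivalent to 40% by 3 years, median survival after recurrence 2.5 years, and a death hazard without recurrence of 0.02 per year. Mean 3-year OS was 0.820, 0.845, 0.872 and 0.941 when 0%, 25%, 50% and 100% of recurring patients were lost at recurrence.

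**Reach of follow-up.** Section 3 allows up to 3 years of participation with no stated start. If that runs from first dose, a full 12-week course plus the 28-day minimum washout leaves at most 36 - (84 + 28)/30.4375 = 32.3 months after surgery. The 36-month row then lies beyond observed follow-up.

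**The case against.** The strongest reply is that the protocol already schedules what is needed. Table 5-1 is said to apply to all subjects, footnote f gives 3-monthly status for anyone in long-term follow-up, and Section 5.4 defines when that follow-up ends without listing recurrence. Section 9 censors at last follow-up, not at the last scheduled contact. On that reading OS is unbiased. This stands, and it limits the point. A reader of the first paragraph of Section 5.4 alone might infer that the trial has no survival follow-up after recurrence. The documents do not support that. They show two incompatible end points for the same contact.

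The bias also needs a chain of events: the narrower sentence prevails, and later deaths are then not recorded. If deaths were picked up passively while survivors stayed censored at recurrence, the bias could run downward. That too argues for stating the rule.

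The later-time figures lean on the assumptions. The 21.4-month lower bound for M equals the median OS that Section 1 reports for cabozantinib after earlier anti-angiogenic therapy. Using instead the 30.3 months it reports for initial treatment lowers the maximum to 8.6 points at 24 months and 16.5 at 36. The table also assumes every recurring patient is lost; at 25% lost, the simulated effect is 0.845 - 0.820 = 2.5 points at 3 years.

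The loss-to-follow-up rule adds little. Remote contact is allowed before recurrence too, and the rule also requires failed phone attempts.

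**Conclusion.** The point holds as an internal contradiction to be reconciled. If the narrower sentence is followed and later deaths go unrecorded, OS censoring is informative and Kaplan-Meier OS is biased upward when mortality is higher after recurrence. The sample-size arithmetic, 5.9 points per uncounted death with none before recurrence, needs no assumed rates. The figures by time do.

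At two of the times Section 9 names, 6 months and 1 year, the illustrated effect is generally below sampling error. At 24 months it is of similar size to sampling error. Only the upper end at 36 months is about twice it, and only if follow-up extends that far. A reader might take 21 points at 3 years as the expected bias; it is the worst corner of an assumed grid with total loss at recurrence.

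If footnote f and the second paragraph of Section 5.4 govern, OS is unaffected. A stop at new therapy alone would still cut DFS follow-up short of its defined event wherever the first paragraph is applied. The primary response analysis is untouched on either reading. This is a minor clarification, worth making because it is cheap and because vital status not collected at the time may be hard to recover.

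**What to change.** Reconcile the two paragraphs of Section 5.4 with Table 5-1 footnote f, and align Section 9:

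- Section 5.4: vital status by chart review or phone continues every 3 months after recurrence or new therapy, until death, withdrawal, loss to follow-up or study end.
- Section 5.4: disease-status follow-up for DFS is not ended by new therapy alone.
- Section 9: OS is censored at the date last known alive.

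While these sections are open, state when the 3 years of participation in Section 3 begin and the time origin for OS, which Section 9 does not give.

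The cost is a few sentences in an amendment and a few extra chart or phone contacts for at most 17 patients. Both routes are already permitted, and no visits or scans are added.
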